### 10.3.2 Analysis of the Primary Efficacy Endpoint(s)

### **Primary**

1. Diagnostic accuracy of Nanoscope compared to conventional arthroscope.

Diagnostic accuracy of the Arthrex Nanoscope will be described as a incidence/percentage compared to the diagnosis determined by wrist arthroscopy with conventional instruments.

### 10.3.3 Analysis of the Secondary Endpoint(s)

### Secondary

- 1. Incidence of change in intervention.
- 2. Surgeon rated ease of use.
- 3. Surgeon rated confidence of diagnosis.
- 4. Correlation between pre-operative MRI findings and arthroscopic findings.

Secondary endpoints will be described using incidence/percentage. A two-tailed Student's T-tests will be employed to compare the means of surgeon-rated outcomes between the Arthrex NanoScrope and conventional instruments groups with a p value of .05.

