### 5.4 Strategies for Recruitment and Retention

Patients will be recruited from investigator clinical practices. The recruitment plan does not propose to use any NYULMC media services or social media. Patients with clinically diagnosed wrist pathology undergoing wrist arthroscopy will be identified by the attending physician and recruited for the study in the office visit when surgery is indicated/scheduled or in the pre-operative area on the day of surgery. The nature of the information the subjects will be asked to give about themselves will include objective information relevant to their wrist injury. Only the individuals listed in the protocol will have access to the patients study.

As this study does not require long-term patient participation, there are no relevant modalities necessary to enhance participant retention.

The target sample size is 34 patients, recruited from the investigators clinical practice.

Study number: i20-00356 Page 14 Version: June 8, 2020

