### 6.3.2 Procedures for Training of Clinicians on Procedural Intervention

The intervention will be standardized by having a single operator (attending) perform the diagnostic arthroscopy with the Arthrex NanoScope and conventional instruments. The diagnostic arthroscopy will be performed in a stepwise manner evaluating the ligaments and articular surfaces of the wrist.

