# 7.1 Study Procedures/Evaluations

### 7.1.1 Study Specific Procedures

- Patients undergoing wrist arthroscopy for diagnostic evaluation and treatment of a wrist injury will be enrolled pre-operatively following a
  discussion of the study, risks, benefits, and informed consent.
- All patients will be positioned supine and placed in an upper extremity traction tower with the shoulder abducted, elbow flexed to 90 degrees, forearm in neutral position.
- Standard arthroscopic portals will be made for viewing, instrumentation, inflow, and outflow: 3-4 portal, 6-R portal, midcarpal ulnar (MCU) portal, +/- midcarpal radial (MCR) portal, +/- 6-U portal.
- A diagnostic arthroscopy will be performed with the Arthrex NanoScope.
  - Structures evaluated:
    - Radial styloid
    - Proximal scaphoid articular cartilage
    - Scaphoid fossa
    - Radioscaphocapitate (RSC) ligament
    - Long radiolunate (LRL) ligament
    - Short radiolunate (SRL) ligament
    - Scapholunate (SL) ligament
    - Proximal lunate articular cartilage
    - Lunate fossa
    - Triangular fibrocartilage complex (TFCC)
  - The attending performing the diagnostic arthroscopy will make an initial diagnostic assessment based on the presence/location/severity of synovitis, articular cartilage integrity, ligament injury and determine the intended treatment.
- A diagnostic arthroscopy will then be performed with the standard arthroscopic instruments.
  - Structures evaluated:
    - Radial styloid
    - Proximal scaphoid articular cartilage
    - Scaphoid fossa
    - Radioscaphocapitate (RSC) ligament
    - Long radiolunate (LRL) ligament
    - Short radiolunate (SRL) ligament
    - Scapholunate (SL) ligament
    - Proximal lunate articular cartilage
    - Lunate fossa
    - Triangular fibrocartilage complex (TFCC)
  - The attending performing the diagnostic arthroscopy will make the final diagnostic assessment based on the presence/location/severity of synovitis, articular cartilage integrity, and ligament injury and determine the final treatment.

Study number: i20-00356 Page 17 Version: June 8, 2020

- Following the procedure the surgeon will perform a short questionnaire.
  - Surgeon rated visualization. (5 point scale)
  - Surgeon-rated ease of use. (5 point scale)
  - o Surgeon-rated diagnostic confidence. (5 point scale)
- The initial diagnostic assessment and final diagnostic assessment will be compared to determine diagnostic accuracy of the Arthrex NanoScope.

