# 9 Clinical Monitoring

Clinical site monitoring is conducted to ensure that the rights and well-being of human subjects are protected, that the reported trial data are accurate, complete, and verifiable, and that the conduct of the trial is in compliance with the currently approved protocol/amendment(s), with GCP, and with applicable regulatory requirement(s).

- The PI will conduct on-site monitoring for initial assessment with a comprehensive review of the data.
- Independent audits will be conducted by the sub-investigators to ensure monitoring practices are performed consistently across all participating sites.
- Each clinical site will perform internal quality management of study conduct, data collection, documentation and completion. An individualized quality management plan will be developed to describe a site's quality management.

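### The t-test on surgeon ratings ignores which surgeon gave them, and the number of surgeons is not stated, so its p-value may be too small or too large, and with one surgeon it speaks only for that surgeon

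*Combined protocol and SAP*

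**What the plan says.** Section 10.3.3 sets the analysis of ease of use and diagnostic confidence: "A two-tailed Student's T-tests will be employed to compare the means of surgeon-rated outcomes between the Arthrex NanoScrope and conventional instruments groups". The level is 0.05 ("conventional instruments groups with a p value of .05"). Section 10.3.1 gives the same general method. Neither section mentions pairing, a surgeon term, clustering or a summary by surgeon.

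Under 7.1.1 the surgeon fills in a short questionnaire after the procedure, with 5-point items. The study schematic lists ease of use and confidence under both the NanoScope and the conventional assessment. So 34 patients give 34 ratings per instrument, or 68 per item.

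The number of raters is left open:

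- Section 6.3.2: "The intervention will be standardized by having a single operator (attending) perform the diagnostic arthroscopy with the Arthrex NanoScope and conventional instruments". This can mean one attending for each case or one for the whole study.
- Section 5.4 begins "Patients will be recruited from investigator clinical practices" and ends "The target sample size is 34 patients, recruited from the investigators clinical practice", moving from plural to singular.
- Section 5.6 lists four sites of one institution, while 4.1 calls the study single center and 8.5 says it is not multi-center.
- Section 9 has sub-investigators audit in order to "ensure monitoring practices are performed consistently across all participating sites". There they act as auditors, not raters.

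Section 4.2.2 wants to learn how many uses a surgeon needs to become familiar with the instruments, and 4.2.3 looks for a learning curve. The plan therefore itself expects ratings to depend on the rater.

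**The concern.** An ease-of-use score is an opinion. A surgeon who likes or dislikes the NanoScope shifts the rating difference in every wrist that surgeon operates on, so 34 wrists do not supply 34 independent opinions of the instrument. Moving to a paired test would not cure this, because the surgeon's preference is part of the within-wrist difference.

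At stake is the reading of a significant result. It could be reported as a property of the instrument when it reflects the preference of one person or of a few. The primary endpoint is described as a percentage in 10.3.2 and does not use this test.

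**Working it through.** **Inputs from the documents.** N = 34 wrists, both instruments in each wrist (10.5.1: each patient is the internal control), two-sided level 0.05. The plan gives no power or precision for the ratings. Its N comes from the sensitivity calculation in 10.4: 31 injured / 0.90 prevalence = 34.4, tabulated as 34. That calculation has no bearing on the ratings.

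**Inputs that are assumptions.** The documents do not give the number of surgeons K, the share ρ of the variance of the within-wrist difference that lies between surgeons (the ICC), or the correlation r between the two ratings of one wrist. Each is varied below.

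**Step 1. What matters in the surgeon effect.** If the same attending rates both instruments, general leniency or severity cancels in the difference. Only variation between surgeons in the *instrument difference* remains, and ρ measures that alone.

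**Step 2. Paired test that ignores surgeon.** With equal caseloads the variance of the mean difference is multiplied by 1 + (34/K − 1)ρ. At ρ = 0.10:

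- K = 2: 1 + 16 × 0.10 = 2.60; effective sample size 34/2.60 = 13.1
- K = 3: 1 + 10.33 × 0.10 = 2.03; 16.7
- K = 4: 1 + 7.5 × 0.10 = 1.75; 19.4
- K = 6: 1 + 4.67 × 0.10 = 1.47; 23.2

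**Step 3. Unpaired test as written.** It takes the variance of the difference in means as 2s²/34. The true value is 2s²(1 − r)/34 times the Step 2 factor. The ratio of true to assumed variance is therefore about (1 − r)[1 + (34/K − 1)ρ]. Below 1 the p-value is too large; above 1 it is too small. At r = 0.5:

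| ρ | K = 2 | K = 3 | K = 4 | K = 6 |
|---|---|---|---|---|
| 0 | 0.50 | 0.50 | 0.50 | 0.50 |
| 0.10 | 1.30 | 1.02 | 0.88 | 0.73 |
| 0.30 | 2.90 | 2.05 | 1.63 | 1.20 |

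The two errors cancel when 1 + (34/K − 1)ρ = 1/(1 − r). At K = 3, ρ = 0.10, r = 0.5 this is 2.03 against 2.

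**Step 4. Type I error by simulation.** Normal ratings, no true instrument difference on average over surgeons, 34 wrists spread evenly over K surgeons, at least 20,000 replicates per cell. A range marks cells where separate runs round differently.

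| Test at nominal 5% | ρ | K = 2 | K = 3 | K = 4 | K = 6 |
|---|---|---|---|---|---|
| Paired | 0 | 5% | 5% | 5% | 5% |
| Paired | 0.10 | 23% | 17% | 14% | 11% |
| Paired | 0.30 | 45% | 35% | 29% | 21% |
| Unpaired, r = 0.5 | 0 | 0.7% | 0.7% | 0.7% | 0.7% |
| Unpaired, r = 0.5 | 0.10 | 9% | 5–6% | 4% | 2–3% |
| Unpaired, r = 0.5 | 0.30 | 26% | 17–18% | 12–13% | 8% |

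These rates are for a conclusion about surgeons in general, with the participating surgeons as a sample of them.

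**Step 5. One surgeon.** With K = 1 the variance between surgeons cannot be estimated from the data at all. More cases sharpen the estimate for that surgeon and say nothing about others.

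**Step 6. Cost of allowing for surgeon.** A t-test on surgeon means holds 5% but has K − 1 degrees of freedom. Its critical values are 12.7 (K = 2), 4.3 (K = 3), 3.2 (K = 4) and 2.6 (K = 6), against about 2.0 as planned. With two or three surgeons the interval would be very wide.

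**The case against.** A reader might infer that the planned p-value is far too small. The documents do not support that. The large percentages belong to a paired test, whereas 10.3.3 describes two groups, which as written is unpaired. Ignoring the pairing pushes the p-value up, and at r = 0.5 and ρ = 0.10 the planned test is near or below its nominal level from three surgeons on. Neither the number of surgeons nor ρ is given, so the direction of the error is open. This stands.

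A reader might also infer that several surgeons rate. That is not established either: four sites of one institution do not prove several operators, and Section 9 mentions sub-investigators only as auditors. With one operator, none of the figures for 2 to 6 surgeons applies. This stands too, but the single-operator wording is ambiguous, and the one-surgeon reading brings its own limit.

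Third, if the participating surgeons are taken as fixed, a paired test on their cases is a legitimate test of their own mean rating difference. With one surgeon it tests whether that surgeon's mean difference is zero. This is correct, and it makes the matter one of how far the conclusion reaches. The plan does not restrict it: 3.2 asks about ease of use and confidence with the NanoScope, not about particular raters.

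Finally, these are secondary ratings for which no power is stated, and 10.1 promises a formal SAP before database lock. The stakes are modest and the analysis can still be specified. Nothing in the present text commits to doing so, or to recording the operator as a study variable.

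**Conclusion.** The concern holds in a limited form. Section 10.3.3 tests operator opinions without regard to who gave them, and the documents leave the number of operators open. With one surgeon the p-value describes that surgeon only. With several, for inference beyond them, a paired test would have a type I error of about 11% to 23% at an assumed ICC of 0.10 with 6 down to 2 surgeons, and about 5% at ICC 0. The unpaired test as written can be conservative or anti-conservative. Accidental cancellation of two errors at some values does not make it valid.

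The sizes rest on assumed K, ICC and within-pair correlation, equal caseloads and normal ratings. What does not rest on them is that the rater count is unstated and the analysis has no place for the surgeon. The consequence is confined to secondary endpoints.

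**What to change.** 1. In 6.3.2, state whether the single operator is per case or for the whole study, and how many attendings will operate.
2. Record the operating surgeon on each CRF, using a study code. Do this during data collection: 13.5 removes the key to the medical record number once collection ends, after which the operator could no longer be traced from the operative report. The familiarity and learning-curve aims in 4.2.2 and 4.2.3 need the same field.
3. In 10.3.3, replace the pooled t-test with the within-wrist rating difference (NanoScope minus conventional), reported overall and by surgeon, with each surgeon's number of cases and mean difference.
4. If there are enough surgeons to estimate variation between them, add an interval that allows for surgeon, either from a model of the differences with a surgeon random effect or from a t-interval over surgeon means. Otherwise state that the result applies only to the participating surgeon or surgeons. The SAP should say in advance how that choice will be made. The exact number of surgeons required is a matter of judgement.

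The cost is one CRF field and a few sentences. The downside is a wider interval or a narrower conclusion.

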### 2.4 Potential Risks & Benefits

### 2.4.1 Known Potential Risks

There are no additional potential risks pertaining to this study involving with the use of the Arthrex NanoScope compared to conventional wrist arthroscopy instruments. The NanoScope will be used with the standard extremity stabilization tower and arthroscopic portals as are used with conventional instruments. The diagnostic arthroscopy using the NanoScope will be performed immediately prior to the diagnostic arthroscopy with the conventional instrumentation. Estimated additional time to perform the diagnostic arthroscopy with the NanoScope is < 5 minutes, which will not result in subjects exposure to risks associated with prolonged anesthesia or surgery. There is also no additional wrist of passing a second device (NanoScope) into the wrist joint, in addition to the conventional arthroscope.

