### 3.2 Secondary Objectives (if applicable)

To determine if the diagnostic accuracy of the Arthrex NanoScope compared to conventional arthroscopic instruments results in a change in intended intervention.

To determine the surgeon-rated ease of use and diagnostic confidence of the Arthrex NanoScope.

To determine the diagnostic correlation between pre-operative MRI and arthroscopy (NanoScope and conventional). The MRI is standard of care for evaluation of ligamentous wrist pathology. It will not be mandated as part of the protocol.

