# 4 Study Design and Endpoints

### 4.1 Description of Study Design

- Prospective cohort study, Diagnostic
- Single cohort
  - Step 1: NanoScope
  - Step 2: Conventional wrist arthroscopy instruments
  - A single cohort study, comparing the diagnostic accuracy of the Arthrex NanoScope to conventional instruments (gold standard).
- Single center
- Instrument: Arthrex NanoScope

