### 10.5 Measures to Minimize Bias

### 10.5.1 Enrollment/Randomization/Masking Procedures

Enrollment will not be randomized. Each patient will serve as an internal control.

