### 10.5.2 Evaluation of Success of Blinding

Blinding is not possible and not indicated for this study design.

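### The between-instrument test of surgeon ratings cannot separate an instrument effect from an order effect, because the NanoScope is always the first look and the conventional scope always the second

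*Combined protocol and SAP*

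**What the plan says.** **Order.** Section 4.1 sets one sequence for the single cohort: "Step 1: NanoScope", then "Step 2: Conventional wrist arthroscopy instruments". Sections 6 and 7.2.2 repeat it. Section 2.4.1 puts no gap between the looks: "The diagnostic arthroscopy using the NanoScope will be performed immediately prior to the diagnostic arthroscopy with the conventional instrumentation". Section 6.3.2 standardises the procedure by "having a single operator (attending) perform the diagnostic arthroscopy with the Arthrex NanoScope and conventional instruments". Under section 7.1.1 both looks cover the same ten structures, and the attending has made an initial diagnosis and chosen an intended treatment before the second look begins.

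**Control of order.** Section 10.5.1: "Enrollment will not be randomized. Each patient will serve as an internal control". Section 10.5.2: "Blinding is not possible and not indicated for this study design". No section mentions order, period or carry-over, or limits how a difference in ratings may be read.

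**Analysis.** Section 10.3.3 specifies a two-tailed t-test at .05, "employed to compare the means of surgeon-rated outcomes between the Arthrex NanoScrope and conventional instruments groups". Section 10.3.1 and the Statistical Analysis row of the Protocol Summary give the same test as a general rule for comparing means between two treatment groups.

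**Purpose.** The objective in section 3.2 is confined to one instrument: "To determine the surgeon-rated ease of use and diagnostic confidence of the Arthrex NanoScope". Sections 2.1 and 2.3 go further and promise to analyse whether ease of use and confidence differ.

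**Timing of ratings.** The Schematic of Study Design lists ease of use and confidence within each scope's own assessment. Section 7.1.1 has the surgeon complete one short questionnaire of 5-point ratings once the procedure is over.

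**The concern.** By the time the conventional scope goes in, the portals have been used, the joint has been inspected structure by structure, and the surgeon has a diagnosis. Any of this could move the ease or confidence recorded for the second look, whichever instrument is used. Confidence is the more exposed rating, since the surgeon is asked how sure they are about a joint they have just assessed. Using each patient as their own control removes differences between patients. It does not remove a difference between first and second look that is common to all patients.

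At stake is how a published p-value is read. A significant result would be taken as a difference between scopes, and a non-significant one as no difference. Either could reflect order alone, or order offsetting a real instrument effect.

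**Working it through.** **1. What the contrast estimates.** Write the rating of a wrist as wrist level + τ × instrument + π × order + error, with instrument and order each coded 0 or 1 (NanoScope 0, conventional 1; first look 0, second look 1). Under section 4.1 the two codes are equal in every observation. The mean conventional-minus-NanoScope difference therefore has expectation τ + π, whether the test is paired or not. A design matrix with columns for intercept, instrument and order has rank 2 of 3 under the planned sequence. With order counterbalanced 17/17 it would have rank 3 of 3. This step uses only the documents.

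**2. What timing changes.** If each scope is rated straight after its own look (the schematic), only the conventional rating is made with prior knowledge of the joint. If both are rated after the procedure (section 7.1.1), the NanoScope rating is also made knowing what the conventional look showed. The mechanism differs, but the sequence is still common to all patients, so the confounding in step 1 stays.

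**3. Illustration of size.** The plan gives no power or sample size for the ratings, so there is no figure of its own to reproduce. Inputs from the documents: n = 34 (section 10.4), two-sided 0.05 (section 10.3.3), 5-point scale (section 7.1.1). Assumed, because the documents give none: no true instrument difference (τ = 0), the second-look shift π, and the SDs.

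- Paired test, SD of the within-wrist difference 0.8: standard error 0.8/√34 = 0.137, 33 degrees of freedom, non-centrality π/0.137.
- Two-group test as written, rating SD 0.8, uncorrelated ratings: standard error 0.8 × √(2/34) = 0.194, 66 degrees of freedom, non-centrality π/0.194.

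Probability of p < 0.05, from the non-central t distribution:

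| Second-look shift (points) | Paired | Two-group |
|---|---|---|
| 0 | 0.05 | 0.05 |
| 0.1 | 0.11 | 0.08 |
| 0.2 | 0.29 | 0.17 |
| 0.25 | 0.42 | 0.25 |
| 0.4 | 0.81 | 0.53 |

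For example, at 0.4 the paired non-centrality is 0.4/0.137 = 2.92, giving 0.81; the two-group value is 0.4/0.194 = 2.06, giving 0.53.

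**4. Sensitivity to the assumptions.** For the paired test, a shift of 0.3 with SD 1.0 gives 0.40, and a shift of 0.4 with SD 0.6 gives 0.97. The two columns of the table rest on different correlations: with rating SD 0.8, a difference SD of 0.8 implies correlation 0.5, since 0.8 × √(2 × (1 − 0.5)) = 0.8, whereas the two-group column takes correlation 0. By simulation at rating SD 0.8 and a shift of 0.25, as the correlation rises from 0 to 0.7 the two-group rate falls from 0.25 to 0.12, and the paired rate rises from 0.24 to 0.63. Pairing does not remove the shift; with positively correlated ratings it usually detects it more often here, because it estimates it more precisely. In the same simulation, counterbalancing order and removing it in the analysis held the rate at about 0.05.

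**The case against.** **The fixed order is deliberate and useful.** It keeps the NanoScope diagnosis free of the reference result. This stands, and it is why the order should not change. It justifies the order for the primary endpoint; it does not make the ratings contrast interpretable.

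**No carry-over has been shown.** This also stands. A reader might infer that the plan will report carry-over as a NanoScope deficit. The documents support only the conditional statement: an order effect, if present, cannot be told apart from an instrument effect. Its size and sign are unknown, and the probabilities above begin at the nominal 0.05.

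**The one-way mechanism depends on timing.** A reader might infer that NanoScope ratings are never made with knowledge of the other look. That fits the schematic but not section 7.1.1, so it cannot be asserted until the two are reconciled.

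**The comparison is a declared purpose.** A reader of section 3.2 alone might infer that section 10.3.3 added a comparison nobody had asked for. Sections 2.1 and 2.3 say otherwise, and the schematic collects both ratings for both scopes. The inconsistency lies between those sections and section 3.2.

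**A caveat might do instead of dropping the test.** The same difference would still be shown descriptively, so this is partly a matter of preference. However, a p-value labelled as instrument against instrument invites the one reading that the design cannot support.

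**Conclusion.** The point holds as a limit on interpretation. Under the planned sequence the ratings test addresses conventional second look against NanoScope first look, and it cannot attribute a difference to the instrument. This follows from the design alone and needs no outside figure. The size of any error is unknown. On the assumed inputs, with no true instrument difference, the chance of a significant paired result runs from 0.05 at no shift to 0.81 at a 0.4-point shift; for the two-group test as written it runs from 0.05 to 0.53. The matter affects secondary, surgeon-rated endpoints only. A reader might extend the argument to the primary accuracy endpoint, but that endpoint is a descriptive percentage judged against the conventional look, which the fixed order serves. The change is advisable but not critical to the trial's main result.

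**What to change.** - Keep the order: NanoScope first, conventional second.
- In sections 10.3.3 and 10.3.1 and in the Protocol Summary, state that the between-instrument significance test is not applied to surgeon ratings. Amending section 10.3.3 alone would leave the general rule in force.
- Report NanoScope ratings with a confidence interval, in line with section 3.2. Show conventional ratings and the within-wrist difference descriptively, labelled *second look after NanoScope*, with no claim of superiority or equivalence of either instrument.
- Align sections 2.1 and 2.3 with this, since both promise an analysis of a difference in ease of use and confidence.
- Reconcile the schematic with section 7.1.1 on when each scope is rated, and state the timing with the results.

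The cost is wording. Section 10.1 leaves the formal SAP to be completed before database lock, and the procedures and sample size do not change; settling the rating time may alter when the form is filled in. The trial gives up a p-value for a comparison that it declared as a purpose but cannot attribute to the instrument.
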